### Quality Scores

Q.1 to Q.4 and Q.6: Quality scores for Signals S.1 to S.4 and S.6 [0 to 100; ≥50 indicates at least acceptable quality]

Q.7 Quality score for Signal S.7, perfusion of the skin [0 to 5.2; Higher values indicate better perfusion leading to better overall quality measurements; no limit defined for acceptable quality]

## 2.4 Primary and secondary endpoints

The primary outcome is defined as at least acceptable (≥50) quality score Q.1 (see 2.3) of heart rate S.1 during a cumulative duration of ≥18/24h per day (midnight to midnight), during ≥7 consecutive days within the 14 days of study duration (binary outcome, measured once).

### A. Secondary feasibility-related outcomes:

A1) At least acceptable quality scores (Q.2 to Q.4 and Q.6/7) of further signals (S.2 to S.4 and S.6/7 (see 2.3) during a cumulative duration of ≥18/24h per day (midnight to midnight), during ≥7 consecutive days within the 14 days of study duration (binary outcomes, measured once).

A2) Cumulative length of time with at least acceptable quality scores Q.1 to Q.4 and Q.6/7 (see 2.3) per study day (continuous outcomes, measured daily).

A4) Primary outcome and secondary outcomes A1 and A2 by skin type according to the Fitzpatrick scale [22] (Appendix 1).

A4) Primary outcome and secondary outcomes A1 and A2 by activity reported by parents and patients if applicable.

A5) Proportion of patients and parents indicating that continuous monitoring with the WD is acceptable per day and per entire study duration (binary outcome, measured daily plus once).

A6) Reasons not to wear the device as reported by parents and by patients if applicable (categorical outcome, measured daily).

A7) Side effects reported by parents and patients, if applicable (categorical outcome, measured daily)

A8) Effort (cumulative number and duration of contacts) per study day for the investigators (continuous outcomes, measured daily).

B) Secondary comparison-related outcomes:

B1) Difference between discrete measurements performed for clinical routine cares of heart rate and the mean of continuously measured signal S.1 (heart rate) within +/-10min at times of the discrete measurement (continuous outcomes, measured potentially multiple times).

B2) Like B1, for percutaneously measured blood oxygenation and signal S.2 (Oxygen Saturation).

B3) Like B1, for respiration rate and signal S.3 (respiration rate).

B4) Like B1, for ear temperature and signal S.4 (core temperature).

B5) Like B1, for ear temperature and signal S.5 (skin temperature).

C) Secondary outcomes for the exploration of specific patterns

C1) Exploration of potential changes in or specific patterns of the measured signals S.1 to S.9 and quality scores Q.1 to Q.6, within 48 hours before and after clinical diagnosis of fever (ear temperature of  $\geq 39.0^{\circ}\text{C}$ , or  $\geq 38.5^{\circ}\text{C}$  if fever is declared for clinical reasons) with or without neutropenia and microbiologically or clinically defined infections, if applicable.

C2) Like C1) for further signals collected with the WD.

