### **2.2 Secondary objectives**

Secondary objectives are related to:

- A. Further feasibility aspects
- B. Comparison of continuously recorded data with results of discrete measurements performed for clinical routine care
- C. Exploration for specific patterns in continuously recorded data before and during episodes of fever and infection

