### **2.4 Signals and scores collected**

Everion® generates signals as vital signs or scores at a frequency of one per second. For this study aggregates will be used. Aggregates are filtered or averaged versions of signals and will be calculated every minute. Aggregates are calculated as quality-weighted average considering all signals whose quality is >50 and then weights each signal by the quality-30. The associated quality score is the average of all quality values >50, if more than 10% of quality values are >50, else it is the average of all quality values <50. For signals without quality scores aggregates are calculated as median value for all signals in the aggregation period of three minutes.

Description of Aggregates	unit	range	ID	Quality Score	name	ID
Signals comparable with discrete measurements						
S.1 HEART RATE	bpm	30-240	6	Q.1	HEART RATE QUALITY	68
S.2 OXYGEN SATURATION	%	60-100	7	Q.2	OXYGEN SATURATION QUALITY	69
S.3 RESPIRATION RATE	bps	2-60	12	Q.3	RESPIRATION RATE QUALITY	75
S.4 CTEMP (Core temperature)	°C	21-46	15	Q.4	CTEMP QUALITY	76
S.5 TEMPERATURE OBJECT (skin temperature)	°C	-10-40	118	-	-	-
Signals for general performance						
S.6 HEART RATE VARIABILITY	ms	2-140	11	Q.6	HEART RATE VARIABILITY QUALITY	74
S.7 PERFUSION INDEX	-	0-5	8	Q.7	PERFUSION INDEX QUALITY	133
S.8 HEALTH SCORE	-	0-100	22	-	-	-
S.9 GSR (Galvanic skin response)	kOhm	0-5	21	-	-	-

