## **4 STATISTICS AND METHODOLOGY**

### **4.1 Statistical analysis plan**

For the primary outcome the proportion of patients and its exact 95% CI will be calculated. Feasibility of continuous monitoring of heart rate in pediatric patients under chemotherapy will be claimed if 15 of 20 patients (75%) fulfil the primary outcome.

For all outcomes, descriptive statistics using standard methods, including graphical methods, will be performed and exact 95% CI for proportions and estimates, where applicable, will be calculated.

For exploratory analyses different methods adapted to data types will be used.

The analyzed dataset contains all included patients. The current version of the R software [23] will be used for analysis.

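### B5 describes skin temperature only by its difference from ear temperature; adding a within-child slope and plot would show whether the signal follows the child's temperature

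*Combined protocol and SAP*

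**What the plan says.** Secondary objective B (section 2.2) is "Comparison of continuously recorded data with results of discrete measurements performed for clinical routine care". Five outcomes carry it out in section 2.4, Primary and secondary endpoints. The template is "B1) Difference between discrete measurements performed for clinical routine cares of heart rate and the mean of continuously measured signal S.1 (heart rate"), averaged over 10 minutes either side of the reading and possibly repeated within a child. Ear temperature is used twice: "B4) Like B1, for ear temperature and signal S.4 (core temperature") and "B5) Like B1, for ear temperature and signal S.5 (skin temperature").

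The signal table (section 2.4, Signals and scores collected) lists core temperature S.4, range 21 to 46 °C, and "S.5 TEMPERATURE OBJECT (skin temperature"), range -10 to 40 °C, as separate signals. Both stand under "Signals comparable with discrete measurements". S.5 has no quality score, so the quality-based outcomes A1 and A2 do not cover it. Section 3.1.1 allows the device on the upper arm or the upper leg.

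For analysis, section 4.1 says "For all outcomes, descriptive statistics using standard methods, including graphical methods, will be performed", with exact confidence intervals where applicable. It names no method specific to B5. Outcome C1 is "Exploration of potential changes in or specific patterns of the measured signals S.1 to S.9" and of the quality scores, in the two days either side of a fever diagnosis; it too has no stated method.

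**The concern.** In B1 to B4 the device and the clinic aim at the same quantity, so a difference away from zero can be read as device error. B5 borrows that form for a signal that the protocol itself separates from core temperature. Here a difference away from zero says only that skin on a limb is not at ear temperature. What a reader wants to know about S.5 is whether it moves when the same child's ear temperature moves.

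S.5 is also among the signals searched for patterns around fever in C1. If B5 is reported only as a mean difference with an SD, a reader may be unable to tell from it whether S.5 responds to body temperature, and B5 will then help little in interpreting C1.

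**Working it through.** **Plan's own figure.** None is given for B5, so there is nothing to reproduce.

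**Inputs.** The form of the outcome (ear reading minus mean S.5) comes from B1 and B5. The SDs, the offset and the mean ear temperature are not in the documents. They are assumed here: ear SD 0.5 to 1.0 °C, SD of an uninformative skin signal 0.5 to 1.5 °C, offset 3 °C, mean ear temperature 37.2 °C.

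**Model.** Let S.5 = a + b × ear + e, with e independent of ear temperature, and D = ear − S.5. Then:

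- mean(D) = mean(ear) − mean(S.5), which does not depend on b once the mean skin level is fixed;
- Var(D) = (1 − b)² × Var(ear) + Var(e).

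Different values of b can therefore give the same mean and the same SD.

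**Simplest case, ear SD 0.8 °C.**

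- Constant sensor (b = 0, no noise): Var(D) = 1 × 0.64 + 0 = 0.64, SD 0.80.
- One-for-one sensor (b = 1, noise SD 0.8): Var(D) = 0 × 0.64 + 0.64 = 0.64, SD 0.80. Its correlation with ear temperature is 0.8 / √(0.64 + 0.64) = 0.71.

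With the same average skin level, both have mean difference 3.00 °C.

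**Noisy uninformative sensor, ear SD 0.8, skin SD 1.0.** Var(D) = 0.64 + 1.00 = 1.64, SD 1.28. Each row below gives mean 3.00 and SD 1.28:

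| Slope b | Noise SD (°C) | Var(D) | Correlation |
|---|---|---|---|
| 0 | 1.00 | 0.64 + 1.00 | 0.00 |
| 0.5 | 1.22 | 0.16 + 1.48 | 0.31 |
| 1 | 1.28 | 0 + 1.64 | 0.53 |
| 2 | 1.00 | 0.64 + 1.00 | 0.85 |

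**Range.** Over the assumed SDs, an uninformative signal gives SD(D) from 0.71 (ear 0.5, skin 0.5) to 1.80 (ear 1.0, skin 1.5). Each is matched exactly by a one-for-one signal whose correlation with ear temperature lies between 0.30 and 0.67.

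**Limits of this result.**

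- If the SD of S.5 itself is known and held at 1.0 (ear SD 0.8), SD(D) = √(1.64 − 1.6r): 1.28 at r = 0, 0.92 at r = 0.5, 0.60 at r = 0.8. Reporting the separate SDs of ear and skin temperature would then recover the overall correlation.
- The slope of D on ear temperature is 1 − b, so D set against the ear reading separates the cases. In a simulation of 200,000 pairs, mean D at ear below 38 °C and at 39 °C or above was 2.77 and 5.11 with no information, and 3.00 and 3.01 with b = 1.

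The paired data therefore hold the answer. The mean and SD of the differences, taken alone, may not.

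**The case against.** A reader might infer that B5 cannot reveal tracking at all. The documents do not support that. B5 is a set of paired differences, not a mean and an SD; section 4.1 leaves the summary open and promises graphical methods, and a plot of differences against the ear reading would show tracking. What stands against the plan is only that no such plot, slope or correlation is named for B5.

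A reader might also infer that B5 is the only check on whether S.5 reflects body temperature. C1 contradicts this: it examines S.5 around fever, and fever is defined there by ear temperature. B5 remains the only outcome that pairs S.5 with individual ear readings, across the whole range of temperatures.

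Nor is the ambiguity in the SD peculiar to B5. A core-temperature sensor stuck at the average ear temperature and an unbiased one-for-one sensor with noise SD 0.8 °C would both give B4 a mean of 0 and an SD of 0.8 °C under the same assumption. What is particular to B5 is that an offset is expected, so the mean difference cannot be read as error.

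Finally, B5 has no acceptance limit, objective B speaks of comparison rather than validation, and the size and spread of the skin-to-ear offset is a legitimate result for a pilot. That is accepted, and it is why the difference should be kept.

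**Conclusion.** The point holds as a minor improvement. B5 describes S.5 only through its difference from a different quantity; the offset is not an error, and the mean and SD of the differences need not show whether S.5 follows the child's temperature. The algebra holds for any SDs. The figures in °C rest on the assumed values above, which the documents neither give nor rule out. How often the ambiguity would arise in practice depends on the actual noise in S.5, which is unknown.

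The consequence is confined to one descriptive secondary outcome in a 20-patient pilot. The feasibility claim (15 of 20 patients meeting the heart-rate criterion) does not depend on it, and the demonstration gives no reason to replace the difference in B1 to B4.

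**What to change.** In section 4.1, add for B5:

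- the slope of S.5 on ear temperature within child, with its 95% CI, from children with at least two pairs. Use either a separate fixed intercept per child, or ear temperature centred on each child's own mean with a random intercept. A random intercept with uncentred ear temperature would mix within-child and between-child association and should be avoided. Working within child also removes offsets that differ between children, for instance from arm or leg placement;
- a plot of S.5 against ear temperature by child;
- the difference, kept and labelled as a description of the offset.

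The cost is a few lines of wording, one model and one figure, all from pairs already planned. Children with a single pair add nothing to the slope, and with 20 children and perhaps few fevers the interval may be wide; the report should then say that tracking was not determined.

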## 2.5 Project design

This is an investigator-initiated, single-center observational pilot study on the feasibility of continuous monitoring of health data with a WD in pediatric patients undergoing chemotherapy of cancer. For patients with cancer, the risk for severe infections is the highest during phases with chemotherapy induced neutropenia. Neutropenia normally last about 10 to 14 days. To detect severe infections earlier, this expected time period with neutropenia, is the period, in which continuous monitoring of health data does make most sense. Therefore, in this study the WD will be studied in the patients for 14 days.

A total of 20 patients will be included, including at least 4 patients <6 years. As this is a feasibility study, a formal sample size calculation has not been performed. However, this sample size allows to assess the primary outcome with clinically meaningful precision and to roughly assess the primary outcome in the group of patients <6 years of age.

## 3 PROJECT POPULATION AND STUDY PROCEDURES

### 3.1 Project population, inclusion and exclusion criteria

Inclusion criteria:

- Chemotherapy treatment because of any malignancy, expected to last  $\geq 1$  month at time of recruitment for myelosuppressive therapy; or at least one cycle of myeloablative therapy requiring autologous hematopoietic stem cell transplantation.
- Age from 1 month to 17.99 years at time of recruitment
- Written informed consent from patients and/or parents

Exclusion criteria:

- Local skin diseases prohibiting wearing of the WD.
- Denied written informed consent from patients and/or parents

### **3.2 Recruitment, screening and informed consent procedure**

This study will be conducted at the Inselspital, Bern University Hospital. Recruitment will take place at the Department of Pediatrics, in the Division of Pediatric Hematology/Oncology. Patients will be screened for eligibility and recruited by a study investigator or treating physician. No specific screening procedures except verifying inclusion/exclusion criteria are needed. Patients will be assessed during a routine outpatient visit, or during hospitalization. Patient recruitment will stop when the aimed number of twenty patients is reached. No payment or compensation will be given to study patients or their parents.

The investigators will explain to the parents/legal representative and the patient if applicable, the nature of the study, its purpose, the procedures involved, the expected duration, the potential risks and benefits and any discomfort it may entail. The parents/legal representative and the patient if applicable, will be informed that the participation in the study is voluntary and that he/she may withdraw from the study at any time and that withdrawal of consent will not affect the subsequent medical assistance and treatment.

The parents/legal representative and the patient if applicable, must be informed that the medical records may be examined by authorized individuals other than their treating physician.

The parents/legal representative and the patient if applicable, will be provided a patient information sheet and a consent form describing the study and providing sufficient information for parents and patients to make an informed decision about their participation in the study. Sufficient time will be given to make the decision.

The formal consent of the parents/legal representative and the patient if applicable, using the approved consent form, must be obtained before the patient is submitted to any study procedure.

If a minor and/or patient under tutelage is capable of judgment, his/her assent is collected (required from the age of 14 years) in addition to the consent of the parents/legal representative on the informed consent form.

The parents/legal representative and the patient if applicable, should read and consider the statement before signing and dating the informed consent form, and should be given a copy of the signed document. The consent form must also be signed and dated by the investigator (or his designee) at the same time as the patient sign, and it will be retained as part of the study records.

### 3.3 Study procedures

Study Periods	Screening	Study visit	Study period	Follow-up
Time (day)	0, 1 or before	0 or 1	1 -14	15 to 17
In- /Exclusion Criteria	x			
Patient Information and Informed Consent	x			
Further patient characteristics	x			
WD distribution		x		
WD instructions		x	x	
Wearing the WD		x	x	
Primary outcome		x	x	
Secondary outcomes		x	x	x
Side effects		x	x	x

#### 3.1.1 Study visit

The study visit will be done during a routine outpatient visit, or during hospitalization. One of the study investigators will distribute the WD, the charger, and if needed the mobile phone to the parents or patient. Parents and/or patients, with no suitable mobile phone, will be provided with a phone for the study time. This phone will not be usable for other purposes than data transfer. Basic characteristics as age, height, weight, thigh and arm circumference and skin type will be assessed at the study visit.

The WD is fitted using body size-appropriate elastic bands and the fitting is controlled by the investigator. Parents and patients if applicable, will be instructed in the handling and charging of the WD. For instructions, the pictures and descriptions provided by the manufacturer on the website, in the “instructions for use” handbook and the information in the study information form will be used. Instruction on how to install the mobile phone app for data transfer will be provided (see 7.2). The WD will be put on the upper arm or, if anatomically reasonable, on the upper leg.

#### 3.1.2 Study period

There will be no additional examinations or procedures performed for this study, specifically no additional discrete measurements of vital signs will be undertaken unless the clinically indicated measurements. Daily activities and temperature measurements if taken during outpatient stay will be recorded on case report forms (CRF) by parents and/or by patients. Questionnaires will be used for the assessment of WD acceptance, side effects and reasons not to wear the device. Parents, patients and members of the treating staff will not be able to access the continuously measured data, in order to avoid any influence on clinical decision making due to these data.

During the measurement period of 14 days no extra visits are planned. During the whole study period, one of the investigators will do a daily data-check, to see if data is recorded properly or not. If no data is recorded or if there are signs for reduced data quality, the parents and/or patients will be contacted by phone. Possible reasons for non-recording or reduced data quality

will be discussed on the phone and instructions will be given to parents and/or patients. During hospital visits calls may be replaced by on ward visits.

Parents and/or patients can contact the study site by phone any time by calling the pediatric oncology ward (24h emergency number) or outpatient ward and ask for assistance with the WD. Investigators are allowed to additionally check data recording, when contacted by parents or patients. Date, number, duration and reason of phone contacts and visits will be noted.

During the study period, parents and/or patients will be in charge for battery charging (approx. 2 hours each day) and data upload via mobile phone app. Parents and/or patients will fill out a CRF daily and note time of charging, connection to the mobile phone, reasons for not wearing the WD, any side effects, activities and temperature measurements, if applicable.

During hospitalization treating staff will perform discrete measurements as clinically indicated and note them in the patient chart. Parents and/or patients will continue to fill out the CRF daily. The charts will be assessed by the investigators to match the recorded data with the data from the WD.

The study period ends regularly for each patient after the planned period of 14 days, in case of intensive care unit admission or at the day of death from any cause, unrelated to the study.

### **3.1.3 Follow-up**

Follow-up period covers 24 hours after the end of the study period. The respective follow-up interview by phone or if applicable during a routine hospital visit will take place 1 to 3 days after the end of the study period.

### **3.4 Withdrawal and discontinuation**

Non-compliance, mainly not wearing or charging the WD, will not lead to exclusion from the study, as this is directly linked to the primary outcome.

In case of withdrawal of informed consent no data will be collected beyond the date of withdrawal except for tracking of side effects for 24 hours after the last time the WD has been worn. The information collected until this date will be used for analysis. This information will be fully anonymized after analysis.

## **4 STATISTICS AND METHODOLOGY**

### **4.1 Statistical analysis plan**

For the primary outcome the proportion of patients and its exact 95% CI will be calculated. Feasibility of continuous monitoring of heart rate in pediatric patients under chemotherapy will be claimed if 15 of 20 patients (75%) fulfil the primary outcome.

For all outcomes, descriptive statistics using standard methods, including graphical methods, will be performed and exact 95% CI for proportions and estimates, where applicable, will be calculated.

For exploratory analyses different methods adapted to data types will be used.

The analyzed dataset contains all included patients. The current version of the R software [23] will be used for analysis.

## 4.2 Handling of missing data

There will be no imputation for missing data. No replacement of drop-outs is done, because the target assessed primary outcome will include drop-outs.

## 4.3 Planned Timetable

There are at least 20 patients under chemotherapy in the study site at any given time point and about 40 patients with newly diagnosed cancer per year. We expect a participation rate of about 75% and thus a study duration of three to four months. We will use ten to twenty in parallel usable WDs.

2019, June	Submission to pediatric IRB Bern
2019, August	Submission to CEC
2019, December	Recruitment of first patient
2020, March	Last patient out
2020, May	Data closure, clean data
2020, July	Data analyzed
2020, October	Manuscript with main results submitted

## 5 REGULATORY ASPECTS AND SAFETY

### 5.1 Local regulations / Declaration of Helsinki

This research project will be conducted in accordance with the protocol, the Declaration of Helsinki [3], the principles of Good Clinical Practice, the Human Research Act (HRA) and the Human Research Ordinance (HRO) [1] as well as other locally relevant regulations. The Project Leader acknowledges his responsibilities as both the Project Leader and the Sponsor.

